4.1 Inclusion Criteria

Eligible women must be able to give appropriate consent or have an appropriate representative available to do so, for participation in the study:

1. Women at least 18 years of age, who will undergo immediate unilateral or bilateral tissue expander breast reconstruction following therapeutic skin-sparing or nipple-sparing mastectomy
2. Women at least 18 years of age, who will undergo immediate bilateral tissue expander breast reconstruction following risk-reduction (prophylactic) skin-sparing or nipple-sparing mastectomy.

4.2 Exclusion Criteria

1. Subjects who are unable to read or speak English
2. Breast reconstruction using the latissimus dorsi flap combined with a tissue expander
3. Documented diagnosis of chronic pain, upper limb spasticity, cervical dystonia, axillary hyperhidrosis, strabismus or blepharospasm
4. Hypersensitivity to any botulinum toxin preparation or to any of the components in the formulation;
5. Infection at the proposed site of injection
6. Pre-existing neuromuscular disorders (including diagnosed myasthenia gravis, Eaton-Lambert syndrome, or amyotrophic lateral sclerosis)
7. Aminoglycosides intake at the time of surgery (these antibiotics can potentiate the effect of BTX-A)
8. Women who are pregnant or breast-feeding
9. Presence of implants from previous breast surgery (could result in higher probability of intraoperative placement of direct implant or subcutaneous placement of tissue expanders)
10. Reported use of Botox within 4 months prior to planned surgical date (could impact the occurrence of adverse events)

4.3 Subject Recruitment, Enrollment and Screening

Potential research subjects will be identified by a member of the patient's treatment team, the principal investigator, or research team at Mayo Clinic. If the investigator is a member of the treatment team, s/he will screen their patient's medical records for suitable research study participants and discuss the study and their potential for enrolling in the research study.

During the initial conversation between the investigator/research staff and the patient, the patient may be asked to provide certain health information that is necessary to the recruitment and enrollment process. The investigator/research staff may also review portions of their medical records at Mayo Clinic in order to further assess eligibility. They will use the information provided by the patient and/or medical record to confirm that the patient is eligible, and to contact the patient regarding study enrollment. If the patient turns out to be ineligible for the research study, the research staff will destroy all information collected on the patient during the initial conversation and medical records review, except for any information that must be maintained for screening log purposes. In most cases, the initial contact with the prospective subject will be conducted either by the treatment team,

investigator or the research staff working in consultation with the treatment team. The recruitment process outlined presents no more than minimal risk to the privacy of the patients who are screened and minimal PHI will be maintained as part of a screening log.

Eligible women will be invited to participate in the study by a member of the patient's surgeon/treatment team or the study's research coordinator at Mayo Clinic, at the time of their preoperative assessment by a plastic surgeon. Electronic medical records will be examined to confirm subjects' eligibility for study participation. During this visit with the plastic surgeon, women who agree to participate will receive information about the study, confidentiality and sharing of information within the research team, as well as an informed consent form. They will have a full opportunity to ask questions about the study and may decide at any point to decline participation in the study. Should patients have additional questions about the study, contact information for a project research coordinator will be provided in the informational documentation. If eligible women do not wish to participate in the study, no further effort will be made to contact them. Prior to enrollment, study participants will undergo a urine pregnancy test to confirm their eligibility.

4.4 Early Withdrawal of Subjects

4.4.1 When and How to Withdraw Subjects

Study participants may be withdrawn from the study prior to the subject completing all of the study related procedures, for the following reasons:

- Ineligibility unknown at the time of enrollment (e.g., inability to proceed with tissue expander reconstruction at the time of mastectomy)
- Nonadherence of enrolled subjects to protocol requirements
- Occurrence of competing events (e.g., patient's best interests)

4.4.2 Data Collection and Follow-up for Withdrawn Subjects

Data collected on study subjects up to the time of withdrawal will remain in the study database and will not be removed, in order for the study to be scientifically valid. If a subject withdraws from the study, removal of already collected data would undermine the scientific, and therefore the ethical, integrity of the research. Such removal of data could also put enrolled subjects, future subjects, and eventual users of marketed products at an unreasonable risk.

Reasonable attempts to follow-up with study participants will be made by the research team. The Principal Investigator will ask each enrolled woman who is withdrawing whether she wishes to provide continued follow-up and further data collection subsequent to her withdrawal from the interventional portion of the study. Under this circumstance, the discussion with the subject would distinguish between study-related interventions and continued follow-up of associated clinical outcome information, such as successful completion of breast reconstruction, obtained through non-invasive chart review, and address the maintenance of privacy and confidentiality of the subject's information.

If a subject withdraws from the interventional portion of a study and does not consent to continued follow-up of associated clinical outcome information, the principal investigator will not access for purposes related to the study the subject's medical record or other confidential records requiring the subject's consent. However, an investigator will review study data related to the subject collected prior to the subject's withdrawal from the study, and will consult public records, such as those establishing survival status.

5 Study Drug

5.1 Description

BOTOX® (onabotulinumtoxinA) for injection is a sterile, vacuum-dried purified botulinum toxin type A, produced from fermentation of Hall strain *Clostridium botulinum* type A, and intended for intramuscular and intradermal use. It is purified from the culture solution by dialysis and a series of acid precipitations to a complex consisting of the neurotoxin, and several accessory proteins. The complex is dissolved in sterile sodium chloride solution containing Albumin Human and is sterile filtered (0.2 microns) prior to filling and vacuum-drying.

One Unit of BOTOX® corresponds to the calculated median intraperitoneal lethal dose (LD50) in mice. The method utilized for performing the assay is specific to Allergan's product, BOTOX®. Due to specific details of this assay such as the vehicle, dilution scheme, and laboratory protocols for the various mouse LD50 assays, Units of biological activity of BOTOX® cannot be compared to nor converted into Units of any other botulinum toxin or any toxin assessed with any other specific assay method. Therefore, differences in species sensitivities to different botulinum neurotoxin serotypes preclude extrapolation of animal-dose activity relationships to human dose estimates. The specific activity of BOTOX® is approximately 20 Units/nanogram of neurotoxin protein complex.

Each vial of BOTOX® (Botulinum Toxin Type A) contains 100 units (U) of *Clostridium botulinum* toxin type A, 0.5 mg albumin (human), and 0.9 mg sodium chloride in a sterile, vacuum-dried form without a preservative. For the purpose of this study, one and two vial(s) of 100 units will be used for the unilateral and bilateral breast reconstructions, respectively. Prior to injection, the research pharmacy service will reconstitute each vacuum-dried vial of BTX-A with non-preserved 0.9% Sodium Chloride Injection USP for a final BTX-A concentration of 2 units/0.1 mL. Thus, **the total volume of solution (BTX-A or placebo) injected in each pectoralis major muscle will be 5 mL (100 units) of BTX-A or 5 mL of 0.9% Sodium Chloride.**

5.2 Treatment Regimen

A single intramuscular injection of 100 units of BTX-A will be done intra-operatively in the pectoralis major muscle. This injection will not be repeated during the course of the study. Thus, women undergoing unilateral tissue expander placement will receive a dose of 100 units of BTX-A, whereas women undergoing bilateral tissue expander placement will receive a dose of 200 units of BTX-A for the purpose of this study.

5.3 Method for Assigning Subjects to Treatment Groups

Methods: Consecutive women who elect to pursue breast reconstruction with tissue expanders will be approached to participate in this study. All consenting subjects will be randomized to receive either a single dose of 100 units of BTX-A per breast, or a placebo. Study participants will not be blinded regarding the use of ADM at the time of surgery.

Treatment group assignment:

STUDY ARMS	ASSIGNED TREATMENT
1	BTX-A +/- ADM
2	Placebo +/- ADM

Randomization and Masking: Treatment blinding and randomization will be carried out in the hospital's Research Pharmacy Service using a program to generate random numbers. The injected solutions of BTX-A and placebo (0.9% Sodium Chloride Injection USP) will be prepared by the pharmacy service to ensure masking. At the time of injection in the pectoralis major muscle, neither the treating surgeon nor the study participants will be aware of group allocation with regards to the use of BTX-A or placebo. All research team members involved in the assessments and analysis of the data will be blinded. Thus, only the pharmacy personnel preparing the syringes will be aware of group assignment (Group A or B).

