3.1 General Design

EXPERIMENTAL DESIGN FOR SPECIFIC AIM#1: To determine the effect of BTX-A on pain and physical well-being during the expansion period in women undergoing subpectoral placement of tissue expanders for two-stage implant-based breast reconstruction.

Research Design: The study design chosen to test our working hypothesis and answer our specific aim is a multi-center, double-blinded, placebo-controlled, prospective, randomized trial. Women at least 18 years of age, who will undergo immediate unilateral or bilateral tissue expander reconstruction, will be recruited to participate in the study.

Consecutively enrolled eligible women will be randomized into one of two different treatment groups, described in section 5.3. Expected duration of subject participation is 4 months.

Study Timeline and Feasibility:

PROPOSED PROJECT TIMETABLE				
AIMS/TASKS	YEAR 01	YEAR 02	YEAR 03	YEAR 04
Specific Aim #1:				→
• Enrollment		→		
• Follow-up		→		
Data Analysis			→	→

For this study, we plan to accrue up to 134 patients in order to obtain a sample size of 128 subjects (64 women per group). Based on annual operative volumes at Mayo Clinic Rochester, and considering that not all plastic surgeons performing tissue expander breast reconstruction will be contributing to

the study, we estimate that approximately 150 women will be eligible for recruitment over a 36-month period, ensuring the feasibility of adequate sample size recruitment (see table below).

Annual numbers of breast reconstructions with tissue expanders at Mayo Clinic Rochester (2008-2010)

Procedure Year	Unilateral tissue expander breast reconstruction	Bilateral tissue expander breast reconstruction	TOTAL
2008	98	123	221
2009	74	111	185
2010 (10 months)	70	107	177

We anticipate that these numbers will remain approximately constant. It is estimated that subjects will be recruited over a 40-month period, and each participant will be followed for 4 months with data collected longitudinally over this period. The last women enrolled in year 1 will be followed for 4months into year 2. Data analysis will commence in year 2.

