3.4 Primary Safety Endpoints

The primary safety endpoints of this study is the incidence of side effects attributable to the injection of BTX-A at doses of 100 units and 200 units, in women undergoing immediate post-mastectomy breast reconstruction with tissue expander(s).

Patients will be advised to inform the Principal Investigator and the study coordinator immediately if they develop any unusual symptoms (including difficulty with swallowing, speaking, or breathing), or if any existing symptom worsens. Patients will also be counseled that if loss of strength, muscle weakness, blurred vision, or drooping eyelids occur, they should avoid driving a car or engaging in other potentially hazardous activities.

At each follow-up visit, the study coordinator will question study subjects about occurrence of adverse events. All serious adverse experiences will be collected and reported. Local side effects of BTX-A injection include a flu-like syndrome that is generally short-lived, dysphagia, and xerostomia. Unintended weakness of the muscle injected or of nearby muscles could also be a negative effect. Other rare potential side effects include muscle soreness, rash, headaches, light-headedness, fever, chills, hypertension, diarrhea, abdominal pain, swallowing and breathing difficulties. Furthermore, the status of wound healing and tissue integrity will be performed at the first postoperative visit for all patients (i.e., at one to two weeks following surgery).

4 Subject Selection Enrollment and Withdrawal

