5.8 Blinding of Study Drug

Treatment blinding and randomization will be done by each site specific Mayo Clinic Research Pharmacy. The research pharmacy will prepare BOTOX® or placebo (0.9% Sodium Chloride Injection USP) according to the randomization. The BOTOX® and placebo will look identical in the syringe after preparation. The labels used for both products are also identical. The final prepared product that will be provided to the surgeon will be labeled "For Investigational Use Only".

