7.2 Statistical Methods**Descriptive Statistics:**

Demographic and medical characteristics will be analyzed for all enrolled subjects. Descriptive statistics will be calculated for all baseline variables. Univariate descriptive statistics and frequency distributions will be calculated, as appropriate for all variables. Baseline values for demographic, clinical, and outcome variables (primary and secondary) will be tabulated separately for the treatment groups. These analyses will help identify whether the randomization was successful in equalizing distributions of these prognostic variables across treatment groups or if confounding variables need to be included as covariates in sensitivity analyses. Putative prognostic variables that will be investigated through these descriptive analyses include variables such as age, body mass index, smoking status, diabetes mellitus, coronary artery disease, hypertension, clinical breast cancer stage, mastectomy weight, initial percent volume expansion (defined as initial intraoperative fill volume divided by manufacturer recommended total tissue expander volume), sentinel lymph node biopsy, axillary dissection, adjuvant therapy factors (e.g., previous and postoperative chemotherapy and radiation), operative time, ADM use.

Handling of Missing Data

Handling of missing data will be done in a number of ways including complete-case analysis and multiple imputations via nearest neighbor, mean value, last value, and zero value carried forward

approaches. Multiple approaches are used so that the sensitivity of results to alteration in multiple imputational assumptions may be assessed.

Primary Hypotheses:

- Pain scores will be at least 25% less, in those who received BTX-A, during the immediate post-operative period compared to those who received saline injections
- Pain scores will be at least 25% less, in those who received BTX-A, during the period of tissue expansion, compared to those who received saline injections
- Physical Well-Being scores during tissue expansion will be higher in those who received BTX-A compared to those who received saline injections

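### Laterality fixes dose and extent of surgery, but the plan names it neither in the allocation (5.3) nor in the analysis (7.2); adjusting for it and stratifying on it would be a cheap, modest gain

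*Combined protocol and SAP*

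**What the plan says.** - **Eligibility.** Section 4.1 admits women "who will undergo immediate unilateral or bilateral tissue expander breast reconstruction following therapeutic skin-sparing or nipple-sparing mastectomy". A second criterion admits bilateral risk-reducing cases.
- **Dose.** Section 5.2 ties dose to laterality: unilateral cases in the active arm receive 100 units, and "women undergoing bilateral tissue expander placement will receive a dose of 200 units of BTX-A for the purpose of this study".
- **Safety endpoint.** Section 3.4, repeated in 7.1, words it by dose: the "incidence of side effects attributable to the injection of BTX-A at doses of 100 units and 200 units". Section 7.2 contains no by-dose analysis.
- **Allocation.** Section 5.3 has the research pharmacy allocate women "using a program to generate random numbers". Section 5.8: "Treatment blinding and randomization will be done by each site specific Mayo Clinic Research Pharmacy". Neither mentions strata, blocks, minimisation or an allocation ratio.
- **Dispensing.** Under 5.4 the pharmacy sends one vial for a unilateral case and two for a bilateral case, so it must know laterality.
- **Target.** Section 3.1 plans to accrue up to 134 women "in order to obtain a sample size of 128 subjects (64 women per group").
- **Analysis.** Section 7.2 compares arms with plain two-sample or contingency-table tests. Baseline tables are used to judge whether covariates are needed in sensitivity analyses. The examples there include "sentinel lymph node biopsy, axillary dissection, adjuvant therapy factors", mastectomy weight, operative time and ADM use. The list is open-ended, and laterality is not on it.

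**The concern.** Laterality determines the number of operated breasts, the number of injected muscles and the total dose. It is a plausible predictor of pain, physical well-being and side effects, although the documents give no data on this. The plan as written neither balances it by design nor adjusts for it in the primary comparison. A chance excess of bilateral surgery in one arm would then sit inside the unadjusted pain difference.

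The safety endpoint raises a second question. Side effects at 200 units can be read fairly only against bilateral placebo women, and those at 100 units only against unilateral placebo women. The plan does not set out that comparison, and nothing in the described allocation protects the comparator counts.

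**Working it through.** **1. The plan's own sample size.** Section 7.1 assumes means of 4.0 and 3.0, SD 2.0, alpha 0.05 (taken as two-sided) and 80% power. A two-sample t-test then needs 64 per arm (power 80.1%). The plan's figure reproduces, as do the other five rows of its table.

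**2. Laterality mix.** From the volume table in 3.1:
- unilateral: 98 + 74 + 70 = 242
- bilateral: 123 + 111 + 107 = 341
- bilateral share: 341/583 = 58.5%

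Applied to 134 women this gives about 56 unilateral and 78 bilateral. It is an assumption that enrolled women follow this mix, because 3.1 says not all surgeons will contribute.

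**3. Imbalance if allocation is unrestricted.** With 64 per arm, the SD of the between-arm difference in bilateral share is √[0.585 × 0.415 × (1/64 + 1/64)] = 0.087, or 8.7 points. Simulating independent 1:1 allocation of 56 unilateral and 78 bilateral women gives:

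| Event | Probability |
|---|---|
| Arms differ by more than 10 points in bilateral share | 24% |
| Arms differ by more than 15 points | 8% |
| Unilateral women split 22:34 or worse, either way | 14% |

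Varying the bilateral share from 50% to 70% moves the 10-point figure only between about 21% and 26%.

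**4. Effect on the pain comparison.** The shift in the observed difference equals the imbalance times the effect of bilateral surgery on pain. The documents do not give that effect, so a range is assumed. For a 10-point imbalance:

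| Assumed bilateral effect (NPIS points) | Shift |
|---|---|
| 0.5 | 0.05 |
| 1 | 0.10 |
| 2 | 0.20 |

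The planned difference is 1.0. Its standard error is 2.0 × √(2/64) = 0.35. With a 1-point bilateral effect, imbalances of 10 to 15 points shift the estimate by 0.10 to 0.15, which is 0.28 to 0.42 of one standard error.

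**5. Gain from adjustment.** If the SD of 2.0 includes the laterality effect, laterality explains a share effect² × 0.585 × 0.415 / 4 of the variance. Power at 64 per arm, against 80.1% unadjusted, becomes:

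| Assumed bilateral effect | Variance explained | Power, adjusted |
|---|---|---|
| 0.5 | 1.5% | 80.7% |
| 1 | 6.1% | 82.5% |
| 2 | 24.3% | 89.7% |

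**6. Unequal arm sizes.** With 134 randomised and before any dropout, t-test power for a difference of 0.5 SD is 81.9% at 67:67, 81.5% at 60:74 and 80.9% at 56:78.

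**7. Within-laterality comparison.** A 22:34 split of unilateral women multiplies the standard error by √(1/22 + 1/34) / √(2/28) = 1.024, an increase of 2.4% over 28:28.

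**8. After stratifying.** With laterality strata and blocks of 4 (an assumed size), simulation of 128 women holds the between-arm difference in bilateral share to about 3 points at most, with an SD of about 1 point. The two arms' unilateral counts differ by at most 2. The sample size does not change.

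**The case against.** The strongest reply is that the plan is silent, not unrestricted. A pharmacy program can produce a blocked or stratified list, and a target of 64 per arm suggests that equal allocation was intended. This stands: every probability in step 3 is conditional on unrestricted allocation. A reader might infer that simple randomisation has been specified, but the text does not say so.

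Second, random imbalance is already covered by the test's error rate. This also stands. A reader might infer a biased treatment effect or a false-positive problem, and neither follows.

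Third, 7.2 has a partial remedy. It tabulates baseline variables by arm, its list is open, and operative time, mastectomy weight and axillary dissection partly capture the extent of surgery. That is fair, but adjustment there is decided after seeing the balance and reaches only sensitivity analyses.

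Fourth, a reader might infer that missing 64 in one arm undermines the trial. Under unrestricted allocation of 134, both arms reach 64 in only 45% of trials, but power stays at or above 80% in about 99% of outcomes, so the consequence is trivial.

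Fifth, the plan defines no formal by-dose test that could become lopsided, and a 2.4% wider standard error is small. That stands too. What remains is that an endpoint worded by dose needs a stated comparator.

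**Conclusion.** The point holds as a modest improvement in precision and interpretability. The factor that sets dose and extent of surgery is not named in the allocation, and the primary tests do not adjust for it. If allocation is unrestricted and the 58.5% bilateral share carries over, imbalance above 10 points occurs in about one trial in four. Its effect on the pain difference is small under an assumed 1-point bilateral effect, and no document shows how strongly laterality predicts either outcome.

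A reader might hope that stratifying would also show whether 200 units behaves differently from 100. It cannot, because dose and laterality are fully tied within the active arm. The documents support only a comparison of active against placebo within each laterality group.

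**What to change.** **Section 7.2, analysis.** Make the primary pain and physical well-being comparisons laterality-adjusted, for example a linear model with arm and laterality, in place of the plain two-sample test. Name laterality in advance instead of leaving it to inspection of baseline balance.

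**Section 7.2, safety.** Report side effects at 100 units against unilateral placebo women and at 200 units against bilateral placebo women, with a note that dose and laterality cannot be separated.

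**Section 5.3.** Specify permuted blocks stratified by laterality, and by site if more than one pharmacy randomises. If this is already the practice, say so.

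If enrolment has begun, the analysis and reporting changes still apply in full. No new data are needed, since the pharmacy already has to know laterality to dispense. The cost is one model term and slightly more list management.
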